9.7 Enrollment

A subject is considered enrolled when the consent process has been finalized. The date the subject (or the subject's authorized/designated representative or guardian) signed the IC and Data Protection Authorization, as required by law, must be documented in the subject's medical records. A log of all subjects enrolled in the study should be maintained. Once consent is obtained, report adverse events/deaths, device deficiencies, study deviations and subject exits as they occur.

After completion of study-related training, designated study personnel may conduct a preliminary assessment of subjects for enrollment into the study. The potential study candidate will be interviewed for their interest in the study and willingness to comply with the study protocol. If the potential study subject is interested and willing to comply, they will be asked to sign the Informed Consent and Research Authorization Form. Upon signing, study personnel will confirm eligibility based on study inclusion and exclusion criteria and will collect baseline information such as:

- Demographics – including date of birth, age, gender, ethnicity
- Medical history including previous interventions and disease state

Subjects who do not meet the eligibility criteria or decline study participation will be considered screen failures. Screen-failed subjects, including reason for exclusion, will be documented on the Screening and Enrollment Log.

Medtronic Business Restricted

9.8 Surgical Procedure

On the day of the Sinus Surgical Procedure the subject should be scheduled giving enough time for study procedures and data collection prior to surgical procedures.

The following information is required to be collected at the surgical procedure visit:

- Lund-Mackay Scores (pre-surgical history)
- Subject completes the baseline SNOT-22 questionnaire
- Physician conducts Endoscopic Examination pre-surgery and grades the sinuses using Lund Kennedy Scores
- Surgical Information: Date of surgery, the surgical location (left, right or both nasal cavities), type of surgery (e.g. turbinectomy, septoplasty, FESS, etc.)
- Collect any Adverse Events and/or device deficiencies
- Physician grades bleeding post-surgery and before packing is inserted using the Boezaart Surgical Field Grading Scale
- Physician grades bleeding post-surgery and after packing is inserted using the Boezaart Surgical Field Grading Scale
- The type of Novapak used and lot number(s)

Subjects may be treated with the Novapak device unilaterally or bilaterally, the number of devices used could be one or two per subject. Therefore, total product used in this study would be a minimum of 75 if a single device is used, to approximately 150 if two devices are used per subject. Note: Physicians are free to modify the size and shape of the device to fit in a unique individual anatomy.

9.9 Scheduled Follow-up Visits

Scheduled visits will occur at day 14 and day 30 post-surgical procedure.

The following information is required to be collected at follow-up visits:

Day 14 visit

- Subject turns in daily irrigations log
- Subject completes the visit SNOT-22 questionnaire
- Collect any Adverse Events and/or device deficiencies
- Physician conducts Endoscopic Examination and grades the sinuses using Lund Kennedy Scores
- Physician conducts adhesion scores and grades the sinuses using the method of Valentine
- Physician debrided adhesions (if necessary)
- Physician removes residual Novapak product if present in the sinuses
- Physician notes any bleeding observed at this examination

Day 30 visit

- Subject completes the visit SNOT-22 questionnaire

Medtronic Business Restricted

- Collect any Adverse Events and/or device deficiencies
- Physician conducts Endoscopic Examination and grades the sinuses using Lund Kennedy Scores
- Physician conducts adhesion scores and grades the sinuses using the method of Valentine
- Physician debrided adhesions (if necessary)

9.10 Unscheduled Follow-up Visits

If a subject returns to the Investigator outside the scheduled follow-up visit window, the Investigator will evaluate the subject according to existing standard of care methods. The reason for the unscheduled follow-up visit will be recorded on the Follow-Up eCRF. Adverse events that present at the time of the visit will also be recorded on the Adverse Event eCRF. Device Deficiencies that present at the time of the visit will also be recorded on the Device Deficiencies eCRF.

Upon the follow-up assessment, the designated study personnel will record the following information:

- Date of Visit
- Reason for unscheduled visit
- Observations from standard of care medical evaluation
- Adverse Events and/or device deficiencies, if applicable

9.11 SNOT-22 Questionnaires

The Sino-Nasal Outcome Test (SNOT-22) is a standardized questionnaire given to assess the subject's severity of symptoms related to their nasal sinuses. The questionnaire will be administered to each subject prior to surgery and then again at day 14 and day 30 visits. A progression in improvement of the scores would indicate that the surgical procedure was successful and the packing material did not hinder this improvement.

9.12 Irrigation Compliance

In order for the Novapak to perform effectively and to fully dissolve as intended the subjects must irrigate their sinuses daily with a saline solution. The subjects will be given a sinus rinse kit with instructions. The kit includes a plastic bottle and packets of Sodium Chloride & Sodium Bicarbonate (USP Grade) which the subjects will make the saline solution using distilled water.

The subjects will log the total daily volume and date of each irrigation. The site coordinator will collect this log at day 14 and inspect for completeness. The number of days where irrigation was done and volume will be recorded.

9.13 Assessment of Efficacy

The following parameters will be used to assess the effectiveness of the Novapak device used according to device indications:

Adhesions – in order to show that Novapak acts a nasal stent to separate tissue or structures compromised by surgical trauma and separate and prevent adhesions between mucosal surfaces in the nasal cavity the study physician will count the number of adhesions present and grade the sinuses using the ordinal scale method published by Valentine 2010.

Control of bleeding – in order to show that Novapak controls minimal bleeding the study physician will grade the bleeding post-surgery and prior to packing using the Boezaart Surgical Field Grading Scale. After inserting the Novapak product with irrigation to hydrate the product the bleeding will be graded again using the same scale.

During the day 14 visit the physician will be asked if any bleeding is observed during the exam and prior to any debridement procedure.

Progression of healing – The Lund Kennedy endoscopic grading system will be used to show that Novapak acts as an adjunct to aid in the natural healing process. The physician will perform an endoscopic exam prior to surgery (to establish a baseline), at day 14 and day 30 visits (to show progressive healing).

Residual Novapak – Novapak dissolves naturally with daily irrigation. Any residual Novapak in the nasal cavity will be recorded at the 14 day visit and compared to the subject compliance to the daily irrigation log.

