Prospective, observational, multi-site, non-controlled, non-randomized, case-series, with adult subjects undergoing nasal/sinus surgery and using Novapak Nasal Sinus Packing and Stent device used as indicated post-operatively with 14-day and 30-day follow-up visits. The study is expected to be conducted at up to 5 study sites located in the US and/or Canada. A minimum of 75 subjects will be enrolled in the study and one device is expected to be used per subject. Study sites that enroll faster than others will be allowed to do so in order to maintain an adequate enrollment rate; however, there is a site maximum enrollment of 60% (45 subjects) of the total enrollment. No known factors have been foreseen that may compromise the outcome of the clinical study or interpretation of the results.

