5.2 Rationale

This study is being conducted to support the safety and treatment effectiveness profile of the Medtronic Novapak Nasal Sinus Packing and Stent device as a post-surgical space-occupying stent for use in patients undergoing nasal/sinus surgery. The data from this study will support the claims stated in the product labeling related to adhesion prevention, control of minimal bleeding and acting as adjunct to aid in the natural healing process.

The single-arm prospective design was chosen as the best option for obtaining the desired data. We rejected designs that use an inappropriate control device that is either non-dissolving, dissolves at a different rate or consistency, or a no treatment arm without packing.

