13.4 Secondary Objective(s)

The secondary objectives are to confirm device effectiveness during the procedure, 2 weeks and 1-month post treatment.

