### 7.1.3 Analysis Sets

The analysis population will include all patients that fulfill inclusion and exclusion criteria and use the Novapak Nasal Sinus Packing and Stent device in their nasal/sinus surgery.

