# Novapak Prospective Observational Clinical Trial Form Statistical Analysis Plan

Version 1.0

Page 7 of 7

- The graded percentage of vertical height of the middle turbinate taken up by the adhesion using an ordinal scale (0-3) from procedure through 1-month post treatment.
- The measure control of bleeding by comparing Boezaart Surgical Field Grading Scale scores post operatively, prior to Novapak insertion and post Novapak insertion.
- The measure of healing by comparing Lund-Kennedy scores before surgery and at 2 weeks and 1-month post treatment.
- The measure of health by comparing subject scores from the SNOT-22 questionnaire before surgery and at 2 weeks and 1-month post treatment.

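### Lund-Kennedy and SNOT-22 change from before surgery cannot show that Novapak aids healing (CIP 9.13) or that packing did not hinder recovery (CIP 9.11)

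*Protocol*

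**What the plan says.** The two statements at issue concern different instruments.

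- **Lund-Kennedy (healing paragraph of CIP 9.13).** "The Lund Kennedy endoscopic grading system will be used to show that Novapak acts as an adjunct to aid in the natural healing process". Its reference point is set in the same paragraph: "The physician will perform an endoscopic exam prior to surgery (to establish a baseline". Later examinations are at day 14 and day 30.
- **SNOT-22 (CIP 9.11).** The questionnaire is given before surgery and at both visits, and "A progression in improvement of the scores would indicate that the surgical procedure was successful and the packing material did not hinder this improvement".

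The SAP analyses both scores as before-after comparisons. For Lund-Kennedy, SAP 7.9.2 lists "The measure of healing by comparing Lund-Kennedy scores before surgery and at 2 weeks and 1-month post treatment"; the SNOT-22 bullet has the same form.

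CIP Section 5 describes the design as "Prospective, observational, multi-site, non-controlled, non-randomized, case-series, with adult subjects undergoing nasal/sinus surgery". SAP 7.1.3 limits the analysis set to eligible patients who "use the Novapak Nasal Sinus Packing and Stent device in their nasal/sinus surgery".

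Two further places carry the healing claim forward. CIP 13.4 says: "The secondary objectives are to confirm device effectiveness during the procedure, 2 weeks and 1-month post treatment". CIP 5.2 says: "The data from this study will support the claims stated in the product labeling related to adhesion prevention, control of minimal bleeding", and its list of claims goes on to include aid in natural healing.

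**The concern.** Both scores are measured first before an operation and then 14 and 30 days after it. Improvement over that interval is expected from the surgery itself, whatever is placed in the nose afterwards. A statement that the device aids healing, or that it did not slow healing, compares the observed course with the course the same patients would have had without the device. This study does not observe that second course.

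The stake is what the report may conclude about one secondary claim. If the two sentences stand, improvement in either score can be cited for a device effect, although it would be seen with an inert packing and could be seen with one that delays recovery. CIP 5.2 intends the data to support labelling claims that include healing, and CIP 3.2 places the study in support of a CE Mark submission. A critical reader of the report would be likely to reject that inference.

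**Working it through.** **No plan figure to reproduce.** CIP 13.5 and SAP 6 say that the minimum of 75 subjects was not derived statistically. The documents give no effect size, SD, margin or success threshold for either score. The question is whether the device effect can be identified at all.

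**Step 1: what happens between baseline and follow-up.**

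| Component | Who has it | Source |
|---|---|---|
| Nasal/sinus surgery and natural healing | every analysed subject | SAP 7.1.3; CIP 9.8 |
| Novapak | every analysed subject | SAP 7.1.3 |
| Daily saline irrigation | required of all | CIP 9.12 |
| Antibiotics, steroids, nasal sprays | may continue | CIP 8.2 |
| Debridement of adhesions | if necessary, day 14 and/or day 30 | CIP 9 |

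**Step 2: what is observed.** For each score,

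observed change = (surgery + natural healing + concomitant care + regression to the mean) + device effect = B + D.

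Only the sum B + D is observed. With no untreated or differently treated group, any value of D fits the data if B is shifted to match. A larger sample makes B + D more precise and leaves the split unknown.

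**Step 3: is B supplied from outside?** Historical data are named as a comparator only for adhesions (CIP 4.1.2; SAP 4.2). None is named for Lund-Kennedy or SNOT-22. CIP 13.1 defines the study population as all eligible consenting patients, and CIP 8.1 expects that some may not receive packing. They are not a planned comparison group, and SAP 7.1.3 excludes them.

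**Step 4: how easily improvement appears without device benefit.** All effects here are assumptions, in SD units of the change score; none is in the documents. Take a two-sided paired t-test at 0.05 with n = 75, so df = 74, critical value 1.993, and noncentrality = (B + D) × √75 = (B + D) × 8.660.

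*Device effect zero (D = 0):*

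| B | Noncentrality | P(significant change) |
|---|---|---|
| 0.2 | 1.732 | 0.40 |
| 0.3 | 2.598 | 0.73 |
| 0.5 | 4.330 | 0.99 |
| 0.8 | 6.928 | >0.999 |

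*Packing slows recovery (D negative):*

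| B | D | B + D | Noncentrality | P(significant improvement) |
|---|---|---|---|---|
| 1.0 | −0.5 | 0.5 | 4.330 | 0.99 |
| 0.8 | −0.4 | 0.4 | 3.464 | 0.93 |

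The first table contradicts the reading in 9.13: a clear improvement does not show that the device helped. The second contradicts the reading in 9.11: it does not show that the packing did not hinder.

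**Step 5: where the argument stops.** The Boezaart grading is done after surgery, immediately before and again after packing (CIP 9.8, 9.13). Its baseline already includes the operation, so the argument above does not carry over to it. Adhesions have a stated historical comparison and are also outside this point.

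**The case against.** The strongest reply is that the study claims little. Analyses of primary and secondary endpoints are descriptive (CIP 13.1), the study is not hypothesis-driven (CIP 13.5), and its purpose is to observe some measures of effectiveness (CIP 3.2). CIP 5.2 discloses the single arm and explains why controls were rejected. Safety is primary. The 9.11 sentence credits surgery first and claims no benefit for the packing. The probabilities above rest on assumed effects and on a test that the plan does not tie to any decision.

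Much of this stands, and it rules out several stronger readings that a reader might infer:

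- *That the study would declare effectiveness confirmed whenever surgery works.* No threshold, margin or success rule is set for either score. SAP 7.2 allows tests as needed but attaches no declaration to them, and effectiveness also covers adhesions, bleeding and residual product.
- *That the whole effectiveness objective in CIP 13.4 fails for the same reason.* It includes effectiveness during the procedure, and the Boezaart baseline is of a different kind.
- *That the SAP asserts the device effect.* SAP 7.9.2 only lists comparisons, and CIP 5.2 speaks of support. Neither contains the faulty inference in the form found in 9.11 and 9.13.
- *That device-specific statements could simply move to residual product or bleeding after packing.* These are uncontrolled too. Residual product depends on irrigation and on the model used, and the bleeding item asks about control after packing while other interventions are allowed (CIP 9.1).
- *That a control arm is required.* The documents justify the single arm, and describing recovery does not need a control.

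The reply does not rescue the two sentences. The descriptive label conflicts with a stated aim to show that the device aids healing, but does not withdraw it. The reason given for having no control explains the design without saying how change could be attributed to the device. Even the modest no-hindrance claim needs the course without packing.

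**Conclusion.** The point holds for two sentences: the Lund-Kennedy claim in CIP 9.13 and the last part of the SNOT-22 sentence in CIP 9.11. Each states an inference that the design cannot support. This conclusion rests only on the documented design: no control group, an analysis set of device users, concurrent care, and no comparator for either score. It needs none of the assumed effect sizes.

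The device's share of the change cannot be given a size from this study. The probabilities in the working, from 0.40 to above 0.999 with an inert device and 0.93 to 0.99 with a harmful one, only illustrate how uninformative improvement would be on this question. They depend on the assumed background change and on a test being run.

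The consequence is limited to the secondary aid-in-healing claim. The primary safety objective and the adhesion and Boezaart bleeding objectives are not affected by this point. It should be corrected, because the sentences are wrong as written and the correction is small.

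**What to change.** Keep the single arm and change the wording:

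1. **CIP 9.13, progression of healing.** Replace the stated aim of showing a device contribution with: *to describe endoscopic healing after surgery with Novapak*.
2. **CIP 9.11.** Delete the closing clause on the packing not hindering improvement, and say that the scores describe symptom recovery after surgery with Novapak.
3. **SAP 7.9.2, Lund-Kennedy and SNOT-22 bullets.** Leave the comparisons as they are and add: *change from baseline reflects surgery, concomitant care and packing together and is not attributed to the device*.
4. **CIP 5.2 and 13.4.** Apply the same limit to the aid-in-healing claim only. Leave the adhesion and Boezaart bleeding objectives unchanged.

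No subjects, visits, data items or analyses are added. The cost is the document amendment and a weaker secondary healing claim.

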9.14 Assessment of Safety

AE information is collected in this study. See Section 11 for further information on the collection of AEs and safety information.

9.15 Recording Data

Data entered must be traceable to source documents. Source documentation is defined as the first time data appear, and may include original documents, data, and records (e.g., hospital records, clinical and office charts, procedure reports, laboratory notes, memoranda, subjects' diaries or evaluation checklists, pharmacy dispensing records, recorded data from automated instruments, copies or transcriptions certified after verification as being accurate copies, microfiches, photographic negatives, microfilm or magnetic media, X-rays, subject files, device data and records kept at the pharmacy, at the laboratories and at medico-technical departments involved in the study).

In general, eCRFs (or paper copies) may not serve as source documents. An exception may be the completed SNOT-22 Questionnaires and endoscopic grading worksheets. Source documentation for data elements not routinely captured in medical records may vary from study site to study site; the study site may use source document worksheets if identified as source documents.

The investigator must ensure the availability of source documents from which the information on the eCRFs was derived. The type and location of source documents should be documented. Where printouts of electronic medical records, are provided as source documents, or where copies of source documents are retained as source documents, those should be certified. Certification must contain (1) the signature of the individual making the copy, (2) the date the copy was made and (3) a statement attesting to the accuracy and completeness of the copy.

The source documents must be made available for monitoring, safety data review or auditing by Medtronic's representative or representatives of the competent authorities and other applicable regulatory agencies.

Medtronic Business Restricted

The CRF may be considered source for the following data collection elements:

- Enrollment Notification
 - Study site assigned subject reference
- Baseline
 - Administrative information
- AE eCRF
 - Date study site became aware of event
 - Relatedness of adverse event
- DD eCRF
 - Date study site became aware of event
- Deviations
 - Reason for deviation
- Device Disposition Log

9.16 Deviation Handling

A study deviation is defined as an event within a study that did not occur according to the CIP or the CTA.

Prior approval by Medtronic is expected in situations where the investigator anticipates, contemplates, or makes a conscious decision to deviate. Prior approval is not required when a deviation is necessary to protect the safety, rights or well-being of a subject in an emergency or in unforeseen situations beyond the investigator's control (e.g. subject failure to attend scheduled follow-up visits, inadvertent loss of data due to computer malfunction, inability to perform required procedures due to subject illness).

For medically justifiable conditions which preempt a subject's ability to complete a study-required procedure, it may be permitted to report only one deviation which will apply to all visits going forward. This may also apply for other unforeseen situations (e.g. the subject permanently refuses to complete a study required procedure and the data will not contribute to the primary end point analysis). However, prior approval from Medtronic is required for such situations.

All study deviations must be reported on the CRF regardless of whether medically justifiable, pre-approved by Medtronic, an inadvertent occurrence, or taken to protect the subject in an emergency. Multiple deviations of the same type at the same visit may be reported on one case report form.

In the event the deviation involves a failure to obtain a subject's consent or is made to protect the life or physical well-being of a subject in an emergency, the deviation must be reported to the IRB/REB as well as Medtronic within five (5) working days. Reporting of all other study deviations should comply with IRB/REB policies and/or local laws and must be reported to Medtronic as soon as possible upon the study site becoming aware of the deviation. Reporting of deviations must comply with IRB/REB policies,

Medtronic Business Restricted

local laws, and/or RA requirements. Refer to Investigator Reports, Section 15.9.1 for geography-specific deviation reporting requirements and timeframes for reporting to Medtronic and/or RAs.

Medtronic is responsible for analyzing deviations, assessing their significance, and identifying any additional corrective and/or preventive actions (e.g. amend the CIP, conduct additional training, terminate the investigation). Repetitive or serious investigator compliance issues may result in initiation of a corrective action plan with the investigator and study site, and in some cases, may necessitate suspending enrollment until the problem is resolved or ultimately terminating the investigator's participation in the study. Medtronic will provide study site-specific reports to investigators summarizing information on deviations that occurred at the investigational study site as needed.

Examples of study deviations include but are not limited to:

- Failure to obtain proper IC
- Failure to collect required study data
- Inclusion/exclusion criteria not met
- Visit conducted outside of scheduled visit window
- Device not used per labeling

